Study size	
Based on the patient count estimations, the expected total study size in the four target countries (Denmark, France, Spain, and Sweden) is about 850 children under two years with VTE, with approximately 280 of them using rivaroxaban oral suspension.
 
All children from the target population present in the data sources will be analysed.

Data analysis	
Descriptive analyses by data source
 
Categorical variables will be presented as counts (n) and proportions (%), with 95% confidence intervals (CI) where relevant. Continuous variables will be presented as means with standard deviation and as medians with interquartile range, where appropriate.
 
The following descriptive analyses will be presented:
 
 • Patients' characteristics according to exposure category (rivaroxaban or SOC), with stratification on the status of exposure, i.e., initiators versus switchers • Drug utilization patterns of initial therapy and maintenance therapy (dose, frequency, route of administration, treatment duration, treatment switch)

	
 • Crude incidence rate, cumulative incidence and Kaplan-Meier analysis of the safety and effectiveness outcomes, using an as-treated exposure definition. Sensitivity analyses will be applied for the exposure (considering only the first treatment agent episode) and for the safety and effectiveness outcomes (considering a more restrictive definition). 
Combined descriptive analyses of aggregated data across data sources
 
 • Characteristics of patients and drug use patterns • Safety and effectiveness outcomes (if sample size allows)
Milestones	
Start of study period: market entry date of rivaroxaban oral suspension in each country
 
Start of data collection: 12 months from the PRAC endorsement of the full study protocol
 
End of data collection: Q2 2029
 
Study progress report: Annually, from Q4 2023 to Q4 2027
 
Final report of study results: Estimated Q4 2029
 
The annual progress reports will allow to monitor the uptake of rivaroxaban oral suspension and follow-up the number of patients for the study population as well as opportunities to finalize the study earlier.

5. Amendments

None

6. Milestones

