- ^a. Patients will be followed in two exposure categories, rivaroxaban or SOC (heparins, VKAs, other DOACs). Treatment episode of rivaroxaban oral suspension OR SOC defined by cumulative days of supply from consecutive dispensations, until discontinuation (grace period of 30 days allowed and 30-day carry-over period) or switch to other anticoagulation therapy. During an anticoagulation treatment period, switches from SOC to rivaroxaban and vice versa are allowed.
- ^b. Baseline conditions: demographics, characteristics of the index VTE, co-morbidities, prior treatment.
- ^c. Censoring criteria will be the earliest of: discontinuation of all study drugs (rivaroxaban and SOC), death, disenrollment/de-registering/emigration, last available data, end of the study period.

Adapted from Schneeweiss S et al. Graphical Depiction of Longitudinal Study Designs in Health Care Databases. *Ann Intern Med.* 2019 Mar 19;170(6):398-406.

Figure 1 Study design diagram

The strengths of this study design to answer the research question include:

- Use of population-based secondary health data sources which capture observational data from routine clinical practice. This avoids the possibility to influence prescribing behaviour and reduces the risk of selection bias or recall bias due to the secondary nature of the data. The results will reflect prescribing behaviour and risk of outcomes in real-world clinical practice.
- Selection of secondary health data sources providing large population coverage and/or population size, as well as broad coverage of health care settings from different geographical locations and health care systems. This will help: i) maximizing study size in this rare clinical condition, ii) providing ability to identify and follow-up the study population by capturing relevant diagnoses, drugs, and outcomes, and iii) ensuring representativeness for the general target population.
- Use of a new user design, where the at-risk period begins on the date of first observed record of anticoagulation therapy (index date), instead of the preceding VTE date.
- Contextualization of the use of and outcomes with rivaroxaban oral suspension by available contemporary treatment options.

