9.2.2. Study time frame

9.2.2.1. Index date and follow-up

The index date will be the day of initiation of any anticoagulation therapy (rivaroxaban oral suspension or SOC). Patients will be assigned to two exposure categories, rivaroxaban or SOC, according to their actual use of the respective anticoagulation therapy. They may contribute time at risk to more than one exposure category if they switch from one to the other. More specifically, patients will be allowed to switch multiple times between SOC and rivaroxaban and contribute time accordingly to both exposure categories, as long as the same anticoagulant treatment period is continuing.

Patients will be followed from the index date to the earliest of the following censoring criteria:

- End of the anticoagulation treatment period, i.e., discontinuation of all study drugs (rivaroxaban and SOC),
- Death,
- Disenrollment/de-registering/emigration or last available data,

- End of the study period.

Moreover, patients will be followed until the first occurrence of each safety/effectiveness outcome event, with time at risk defined separately for each outcome analysis.

If patients have another initiation of anticoagulant therapy (SOC or rivaroxaban) for a VTE diagnosis before the age of two years, i.e., another qualifying anticoagulant treatment period for a recurrent VTE observed during the inclusion period for which they fulfil all inclusion and exclusion criteria (including a 6-month washout period), they will be allowed to enter the study cohort again, with a new index date.

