9.3.2.1.3. Safety outcomes

Potential cases will be identified using diagnostic codes according to the different coding systems in the data sources (preliminary list in [Annex 3](#)). The severity of bleeding might be difficult to determine accurately in secondary health data sources. However, to estimate the severity of bleeding to the extent possible, two co-primary bleeding outcomes with different severity grading will be assessed: Major bleeding or CRNM bleeding. The definitions for major bleeding and CRNM bleeding are based on prior definitions from the International Society on Thrombosis and Haemostasis (ISTH) and definitions used in the EINSTEIN Junior study, with further adaptation to take into account the availability of information in the data sources (6-8). Besides, the definitions for major bleeding and CRNM bleeding will be mutually exclusive.

Major bleeding

Defined as a hospitalization with one of the following primary, related or associated diagnoses:

- Intracranial haemorrhage
- Other critical organ or site bleeding (intrapinal, intraocular, retroperitoneal, intra-articular or pericardial, or intramuscular with compartment syndrome)
- Gastrointestinal bleeding
- Urogenital bleeding

- Other bleeding with a transfusion during hospital stay or resulting in death.

A secondary analysis will be based on an analysis per bleeding site (as described above), if numbers permit.

Clinically Relevant Non-Major (CRNM) bleeding

Defined as bleeding not meeting the criteria for major bleeding, but reported as a primary, related or associated diagnosis during hospitalization.

A sensitivity analysis is planned for major and CRNM bleeding with a more restrictive definition using only main/primary diagnostic codes, excluding secondary diagnostic codes.

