9.7.4. Safety and effectiveness outcomes

Analyses of outcomes will be conducted according to anticoagulation therapy received: rivaroxaban and SOC (including heparins, VKAs, and other DOACs).

Time at risk will consider the exposure of interest (rivaroxaban or SOC) according to the as-treated assumption. For each outcome, the first occurrence for that outcome during time at risk will be identified.

The primary analysis of major bleeding will be based on the outcome definition considering all bleedings at critical sites (or requiring transfusion or resulting in death). A secondary analysis will be based on an analysis per bleeding site if numbers permit.

For each exposure category:

- A crude incidence rate with corresponding 95% CI will be estimated for each outcome.
- The cumulative incidence with 95% CI of each outcome will be estimated at regular time intervals (e.g., at 3, 6, 9 and 12 months).
- Event-free survival of each outcome will be presented graphically with the Kaplan-Meier method.

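### Death is listed as censoring, outcomes are displayed by Kaplan-Meier, and the cumulative incidence estimator is unnamed, so the 3 to 12 month risks will be somewhat overstated if read as one minus Kaplan-Meier

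*Protocol*

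**What the plan says.** **Status of death.** Footnote c to Figure 1 (Section 9.1) reads: "Censoring criteria will be the earliest of: discontinuation of all study drugs (rivaroxaban and SOC), death". Leaving the data source, last available data and the end of the study period follow in the same list. Section 9.2.2.1 repeats the rule: "Patients will be followed from the index date to the earliest of the following censoring criteria", with death as the second bullet.

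**Outcome summaries.** For each exposure category, Section 9.7.4 plans three items:
- a crude incidence rate with 95% CI;
- a risk over time: "The cumulative incidence with 95% CI of each outcome will be estimated at regular time intervals", with 3, 6, 9 and 12 months as examples;
- a graph: "Event-free survival of each outcome will be presented graphically with the Kaplan-Meier method".

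The abstract (Section 4, data analysis row) also lists them separately: "Crude incidence rate, cumulative incidence and Kaplan-Meier analysis of the safety and effectiveness outcomes, using an as-treated exposure definition".

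**Fatal outcomes.** Section 9.3.2.1.3 includes in major bleeding "Other bleeding with a transfusion during hospital stay or resulting in death". Section 9.3.2.2.2 likewise counts VTE that results in death as a recurrence. The deaths censored by rule are therefore those from other causes.

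The protocol names no estimator for the cumulative incidence, makes no provision for competing risks and gives no mortality rate.

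**The concern.** A child who dies of another cause can no longer bleed or have a recurrent VTE. Kaplan-Meier with that death censored treats the child as still able to have the event later, at the same rate as the survivors. One minus that curve is the risk in a setting where nobody dies of other causes. It is never below the proportion of children who actually have the event by a given time, and the gap widens with time.

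Such deaths are plausible here. Section 7.2 says that over 80% of children with VTE have at least one risk factor, and the factors listed include malignancy, congenital heart disease and infection.

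At stake are the absolute risks of bleeding (primary objective) and recurrent VTE (secondary objective) at 3 to 12 months. Section 9.7.1 allows the two exposure categories to be compared in an exploratory sense. Unequal mortality would make the overstatement unequal too.

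**Working it through.** **1. Inputs**
- Bleeding risk for planning, rivaroxaban: 5.6% (Section 9.5.1). It comes from the pivotal trial's main treatment period (Section 7.2), whose length the protocol does not state. Two readings are therefore shown: (A) a 12-month risk; (B) a 3-month risk with constant hazard to 12 months.
- Recurrent VTE, comparator: 3.0% (Section 9.5.1).
- Expected rivaroxaban patients in SNDS: 219 (range 81 to 356), with 12 (range 5 to 20) bleedings (Section 9.5.2).
- Death from other causes on treatment: not given. Assumed range: 1% to 30% at 12 months.

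**2. The plan's own figure**

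Expected events = N × risk: 219 × 0.056 = 12.3 (stated 12), 356 × 0.056 = 19.9 (stated 20) and 81 × 0.056 = 4.5 (stated 5). These reproduce. No figure in the protocol depends on how death is handled.

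**3. Formulas**

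Take constant, independent cause-specific hazards: h for the outcome and d for other-cause death.
- Death censored: 1−KM(t) = 1 − exp(−ht)
- Death competing: CIF(t) = h/(h+d) × [1 − exp(−(h+d)t)]

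**4. Worked example, reading A, t = 12 months**

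h = −ln(1 − 0.056) = 0.0576 per year, so 1−KM = 5.60%.
- 5% mortality: d = −ln(0.95) = 0.0513. CIF = 0.0576/0.1089 × (1 − 0.944 × 0.95) = 0.529 × 0.1032 = 5.46%. Excess 0.14 points.
- 30% mortality: d = −ln(0.70) = 0.3567. CIF = 0.0576/0.4143 × (1 − 0.944 × 0.70) = 0.139 × 0.3392 = 4.72%. Excess 0.88 points.

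For reading B, 1−KM at 12 months = 1 − 0.944⁴ = 20.6%.

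**5. Range**

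| 12-month mortality | A: CIF at 12 m (1−KM 5.60%) | Excess | B: CIF at 12 m (1−KM 20.6%) | Excess | Excess at 3 m, A / B |
|---|---|---|---|---|---|
| 1% | 5.57% | 0.03 | 20.5% | 0.1 | 0.00 / 0.01 |
| 5% | 5.46% | 0.14 | 20.1% | 0.5 | 0.01 / 0.04 |
| 10% | 5.32% | 0.28 | 19.6% | 1.0 | 0.02 / 0.07 |
| 20% | 5.02% | 0.58 | 18.5% | 2.1 | 0.04 / 0.15 |
| 30% | 4.72% | 0.88 | 17.4% | 3.2 | 0.06 / 0.24 |

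Excesses are in percentage points. For recurrent VTE at 3.0% over 12 months, the 12-month excess is 0.08 points at 5% mortality and 0.47 at 30%.

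**6. Sampling error**

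12/219 = 5.5%, Clopper-Pearson 95% CI 2.9% to 9.4%, a half-width of about 3.3 points.

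**7. Unequal mortality, for illustration**

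Under reading B with equal bleeding hazards, 5% mortality in one category and 20% in the other, 1−KM shows 20.6% in both. The actual risks are 20.1% and 18.5%.

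**The case against.** The strongest reply is that the protocol never says the cumulative incidence is one minus Kaplan-Meier. The two are separate items in Section 9.7.4 and in the abstract, and Section 9.7.1 leaves analysis detail to a statistical analysis plan that is not shown. A competing-risk estimator is not excluded, and with one the excess in the 3 to 12 month figures is zero. This stands: a reader might infer that those figures are certain to be overstated, and the text does not support that. What remains is that the protocol itself calls death a censoring event and fixes Kaplan-Meier as the display. The curve carries the problem as written, and so would any cumulative incidence built on the same rule.

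Follow-up must also end at death in any analysis, so the crude incidence rate is unaffected. That stands.

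A reader might infer a large bias. Applying 20% mortality every 3 months under reading B gives 13.8% against 20.6% at 12 months. But that means 1 − 0.8⁴ = 59% dead by 12 months, which nothing in the protocol supports, and it also needs 5.6% to be a 3-month risk.

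A reader might also infer that the bias falls on one exposure category, because sicker children stay on standard of care. The protocol neither says this nor gives mortality by category. It is possible but undocumented.

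Finally, a competing-risk estimate that treats only death as competing still censors discontinuation and switching under the as-treated definition. It is not the full 12-month risk of an unselected child. That is a fair limit on what the fix achieves.

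**Conclusion.** The point holds conditionally. As written, the Kaplan-Meier curves do not display actual risk once children die on treatment of other causes. The cumulative incidences will share the upward bias if they follow the stated censoring rule.

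The expected effect is small: at most about 0.2 points at 3 months; 0.14 to 0.9 points at 12 months for 5% to 30% mortality if 5.6% is a 12-month risk; 0.5 to 3.2 points if it is a 3-month risk carried forward. Only the last extreme approaches the 3.3-point half-width expected for 12/219. These sizes rest on constant, independent hazards and an assumed mortality range. The bias runs in one direction and is cheap to remove, so this is a worthwhile improvement and not a threat to the study's conclusions.

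**What to change.** In Section 9.7.4 and the abstract, state that the cumulative incidence of each outcome is estimated by the Aalen-Johansen method, with death from causes other than that outcome as a competing event. Plot that curve, or keep the Kaplan-Meier graph and label it as a cause-specific display that is not to be read as one minus risk. Keep death as the end of person-time for the crude rates.

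Section 9.4.2 says that the date of death in SNDS is linked for all periods, while causes of death were available only for 2013 to 2015. A workable rule is therefore to treat any death not already counted as an outcome event as the competing event.

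The cost is one sentence and standard software, with no new data. The downside is that the curves differ in form from a conventional Kaplan-Meier display, and that discontinuation and switching remain censored under the as-treated definition, which the report should say.

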9.7.5. Handling of missing data

As a general strategy, no data imputation strategies will be applied to supplement missing data. However, missing values may occur in a small proportion for some variables. In this case, individuals with missing values will be kept in the analysis and a separate category will be created for missing values of that variable.

9.7.6. Sensitivity analysis

9.7.6.1. Sensitivity analysis on exposure

In case of drug switch, the 30-day carry-over period will not be added at the end of the first treatment episode for the main analysis because patients will then contribute time at risk to the switched drug and can only contribute to one exposure category at any given point of time (see [Section 9.3.1](#)). However, patients may actually be using more than one anticoagulant agent at the same time, e.g., when converting from rivaroxaban to VKA. To account for the potential misclassification on exposure during transition and test the impact of the carry-over period, a sensitivity analysis will be conducted, whereby only the first treatment agent episode will be considered, with time at risk including a 30-day carry-over period at the end.

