9.2.3. Selection criteria

9.2.3.1. Inclusion criteria

Participants are eligible to be included in the study only if all of the following criteria apply:

- Evidence of initiation of an anticoagulant therapy (index drug), either rivaroxaban oral suspension or other anticoagulation therapies (heparins, VKAs, other DOACs). Initiation will be defined as a first record of any anticoagulation therapy (rivaroxaban or SOC) without any anticoagulation therapy in the previous 6 months, or since date of birth for children less than 6 months (see codes for anticoagulant drugs in [Annex 3](#)).
- Evidence of a prior VTE diagnosis (index VTE), defined as the presence of at least one primary/main or secondary diagnosis code for VTE recorded in inpatient setting in the previous 30 days (see preliminary list for VTE codes in [Annex 3](#)).
- Age less than two years on index date.
- Baseline period for availability of patient data history in the data source. A minimal baseline period of six months before index date for children aged between six months and two years, and a baseline period since birth for children less than six months of age will be required.

According to its indication, rivaroxaban oral suspension should be used after at least five days of initial parenteral anticoagulation treatment. In order to describe the actual clinical practice in real world settings, there will no requirement on this initial parenteral anticoagulation treatment to include patients in the study population, so patients will be identified independently of this. In theory, all patients receiving rivaroxaban should be switchers. In practice, they may appear as initiating directly with rivaroxaban: the observed initial anticoagulant therapy might be different from the actually received initial therapy, if patients have switched drug during hospital stay and if inpatient drug data is not captured. Depending on availability of inpatient drug data in each data source, the observed initiation of the anticoagulant therapy will be identified either in outpatient or in inpatient setting, as shown in [Figure 2](#) below (see [Section 9.4](#)).

SOC for treatment of VTE in children usually include UFH, LMWH and VKA and may vary across countries. With other DOACs receiving indication for VTE in paediatrics, SOC may also evolve over time.

Figure 2 Visualization of patient journey

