 - For all agents, a grace period of 30 days will be used. Thus, a treatment episode will be considered discontinued if a gap >30-day grace period is observed between consecutive prescriptions of the same agent. A 30-day period will be added at the end of the treatment episode of each agent to account for a carry-over effect unless a drug switch is observed.
- **Drug switch:** defined whenever a prescription of another anticoagulant agent is recorded during a treatment episode of the prior anticoagulant agent.
- Treatment episodes for the individual SOC agents that are overlapping or separated by less than the 30-day grace period will be collapsed into a single SOC treatment episode.

- **Anticoagulant treatment period:** defined as a sequence of treatment episodes of rivaroxaban and SOC, i.e., from the initial treatment episode of the first agent at index date and all potential consecutive switch(es) to other agents. An anticoagulation treatment period will be considered discontinued when all study drugs of interest are discontinued.

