9.7.3. Drug utilization patterns

Drug utilization patterns will be described according to the variables mentioned in [Section 9.3.2.1.2](#).

Exposure duration will be classified into two categories: ≤ 3 months and > 3 months.

A Sankey diagram or equivalent will be used to describe at the patient-level the sequence over time of successive anticoagulant agents/classes.

Drug utilization patterns will also be described over time during the study period to identify potential time trends (secondary objective).

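### The only exposure sensitivity analysis (Protocol 9.7.6.1) changes two things at once, so it does not isolate the carry-over effect it sets out to test, and it drops rivaroxaban time for every observed SOC-to-rivaroxaban switcher

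*Protocol*

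**What the plan says.** In the main analysis (Protocol 9.3.1), "A 30-day period will be added at the end of the treatment episode of each agent to account for a carry-over effect", with an exception at a switch. Section 9.7.6.1 confirms the exception: "In case of drug switch, the 30-day carry-over period will not be added at the end of the first treatment episode for the main analysis". From the switch onward, time belongs to the new drug.

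Section 9.7.6.1 gives the sensitivity analysis two purposes: "To account for the potential misclassification on exposure during transition and test the impact of the carry-over period". The rule is one "whereby only the first treatment agent episode will be considered, with time at risk including a 30-day carry-over period at the end". The abstract and section 9.9 repeat the first-episode restriction, and 9.9 presents it as the check on the main exposure assumption. The other sensitivity analyses in 9.7.6 concern outcome definitions only.

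On the order of treatment, section 9.2.3.1 says "In theory, all patients receiving rivaroxaban should be switchers". It then adds that in practice children may appear to start directly on rivaroxaban. Section 9.9 explains why: SNDS and the Swedish registers hold no inpatient drug data, so a child switched in hospital shows rivaroxaban as the first observed agent. The Danish hospital medication register and the SIDIAP hospital linkage are expected to show the parenteral start.

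**The concern.** A check on carry-over should change the carry-over and nothing else. This one also restricts the data to a single episode per child, so whatever moves could be due to either change.

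The restriction also falls unevenly. The example in 9.7.6.1 is a child converting from rivaroxaban to a VKA, where the first agent is rivaroxaban. The sequence the protocol expects for rivaroxaban users runs the other way, from parenteral treatment to rivaroxaban. When that switch is observed, the first agent is SOC. The child's rivaroxaban time disappears, and the 30 added days of SOC time coincide with the first 30 days on rivaroxaban. In a study requested to address bleeding risk, the check then moves early events from the study drug to the comparator category and discards the later ones.

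**Working it through.** **What changes against the main analysis**

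| Child | Main analysis | 9.7.6.1 |
|---|---|---|
| One episode, no switch | episode + 30 days | the same |
| Observed SOC to rivaroxaban | SOC to switch; rivaroxaban + 30 days | SOC + 30 days after switch; no rivaroxaban time |
| Observed rivaroxaban to SOC | rivaroxaban to switch; SOC + 30 days | rivaroxaban + 30 days after switch; no SOC time |

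In both switch rows, two features change together. In the first row none does. No row uses a length other than 30 days.

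**The plan's own counts** (9.5.2, Table 6). The mean market share is (10 + 32 + 38 + 42 + 50 + 30)/6 = 33.67%.

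- Denmark: 52 × 0.3367 = 17.5 (stated 18)
- SNDS: 650 × 0.3367 = 218.8 (219)
- SIDIAP: 45 × 0.3367 = 15.2 (15)
- Sweden: 98 × 0.3367 = 33.0 (33)
- Overall: 846 × 0.3367 = 284.8 (285)
- SNDS rivaroxaban bleeds, major and CRNM together: 219 × 0.056 = 12.3 (12)

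All reproduce.

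**Rivaroxaban users lost.** Assume every Danish and SIDIAP user has an observed parenteral start: 18 + 15 = 33 of 285, or 11.6%. The remaining 219 + 33 = 252 (88.4%) are in SNDS and Sweden. Let s be the share of these with an SOC record before rivaroxaban. The protocol gives no value for s, so it is varied.

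- Share lost = (33 + 252s)/285
- SNDS rivaroxaban bleeds retained = 12.26 × (1 − s), assuming the same bleeding risk in retained and lost users

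| s | Users lost | SNDS bleeds retained |
|---|---|---|
| 0 | 33/285 = 11.6% | 12.3 |
| 0.25 | 96/285 = 33.7% | 9.2 |
| 0.5 | 159/285 = 55.8% | 6.1 |
| 1 | 285/285 = 100% | 0 |

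Half of all users are lost at s = 1 − 142.5/252 = 43.5%. The retained SNDS count falls below the French threshold of 10 (9.7.8) at s = 1 − 10/12.26 = 18.5%. At the protocol's lowest SNDS estimate the count is already below 10 with nothing lost (81 × 0.056 = 4.5). At the highest (356 × 0.056 = 19.9) the crossing is at s = 1 − 10/19.94 = 49.8%.

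**Bleeds moved to SOC.** Assume constant hazard over a rivaroxaban course of D days, so that a fraction 30/D of bleeds falls in the first 30 days. With D = 90:

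- Denmark and SIDIAP: 33 × 0.056 × 30/90 = 0.6
- SNDS: 12.26 × s × 30/90 = 1.0 at s = 0.25, 2.0 at s = 0.5 and 4.1 at s = 1

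At s = 0.5 the SNDS figure is 3.1 for D = 60 and 1.0 for D = 180.

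**The case against.** The best defence is that the analysis does what its text describes. The main analysis gives post-switch time to the new drug, and the alternative gives 30 days to the old one because the two may overlap. That contrast is deliberate, and it means the carry-over at a switch is tested in some form. It would therefore be wrong to infer that the carry-over is never tested. What stands is that its effect is not separated from the loss of later episodes, and that its length is fixed.

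A reader might also infer from section 9.2.3.1 that the check removes most rivaroxaban exposure. The documents do not support that. In SNDS and Sweden, with 88% of expected users, a child switched in hospital appears as a rivaroxaban initiator and keeps that first episode. Losing most users needs s above 43.5%. The near-certain loss is in Denmark and SIDIAP, where outcome counts are expected to be suppressed anyway. Even there it depends on access: Annex 3 describes the Danish hospital register as not yet released, and Table 3 lists the SIDIAP linkage as possible. Against this, section 9.9 accepts that some children in SNDS and Sweden will still be on parenteral treatment at their first outpatient record, so s = 0 cannot be assumed.

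A third inference is that carry-over days inflate duration of use and push courses past the 3-month cut in 9.7.3. Footnote a to Figure 1 could be read that way, since it runs an episode "until discontinuation (grace period of 30 days allowed and 30-day carry-over period" or a switch. But the footnote is condensed. Section 9.3.1 derives duration from days of supply or prescription intervals and adds the 30 days after the episode, and 9.7.6.1 ties carry-over to time at risk. No duration error is shown.

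Finally, the study is descriptive with no confirmatory comparison. That limits the consequence, but this is still its only robustness check on exposure.

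**Conclusion.** The point holds as a design fault in 9.7.6.1. The check bundles two changes, leaves single-episode children untouched and fixes the length at 30 days, so it cannot deliver its second stated aim. For observed SOC-to-rivaroxaban switchers it deletes rivaroxaban time and assigns early rivaroxaban bleeds to SOC.

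The size depends on s, which the protocol does not give. The loss is about 12% of expected rivaroxaban users at s = 0, if inpatient drug data are obtained in Denmark and SIDIAP, 34% at s = 0.25 and 56% at s = 0.5. In SNDS, the only source expected to support outcome analysis, the average estimate of retained rivaroxaban bleeds becomes unreportable once s passes about 18.5%. Major and CRNM bleeding are separate outcomes, so each count is no larger than the combined figure used here. The bleed figures rest on the protocol's 5.6% risk. The number moved to SOC also assumes constant hazard and a 90-day course.

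**What to change.** Rewrite 9.7.6.1 so that each run changes one thing.

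1. Keep all episodes as in the main analysis and vary only the carry-over: 0 days against 30, optionally with one intermediate length.
2. In a separate run, keep all episodes and change only the attribution of the 30 days after a switch, to the prior agent instead of the new one.
3. If a first-episode analysis is kept, use the first episode of each exposure category (first rivaroxaban, first SOC) and report the number of rivaroxaban users retained per source.

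The abstract and section 9.9 need matching wording. The cost is a protocol and SAP wording change before extraction and a few reruns of the same code with different parameters. Some cells will probably be suppressed. For that reason a separate stratum for the 30 days after a switch is not proposed: in SNDS it would hold about 4 expected rivaroxaban bleeds even at s = 1 (90-day course), against a threshold of 10.
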